2.7 Risk/Benefit Assessment

All mCRC patients enrolled into this randomized trial will receive therapy according to the current *RAS* status and approval status of the drugs employed. Thus, it is not expected that study participants are under-treated or are exposed to additional risks from the treatment. Tumor staging will also be performed in line with the guidelines for stage IV patients in both randomization arms.

Blood sampling for liquid biopsy is collected during routine blood sampling before chemotherapeutic treatment. No additional invasive methods are used.

Patients in the experimental arm additionally may have a benefit of treatment adaptations compared to control arm.

However, due to limited clinical data supporting this innovative study design, two stopping rules are included to increase patient safety:

1. After randomization of 20 patients, further enrollment into the study will be paused. Liquid biopsy samples from the first 20 screened patients will be analyzed in parallel by 2 laboratories. In case of concordant results, the study will continue. In case of discordant results, DSMB will make recommendations for further progress of the study. Additionally, tumor-specific genes will be analyzed to define ctDNA in the samples. This should primarily be performed by measurement of "house-keeping genes" that are identified by Next Generation Sequencing (NGS) of baseline tumor tissue or if not applicable by methylation analysis of promotor region of the genes WIF1 and NPY which serve as surrogate markers for tumor cells.

Also for the first 20 patients showing conversion to *RAS* wild-type in liquid biopsy during screening, at two time points, tumor material assessed locally, as well as a liquid biopsy sample will be analyzed comparatively for *RAS* mutation / wild-type to assess agreement between the analysis methods. This will be done at baseline and once during screening when *RAS* wild-type is detected in liquid biopsy. For the second comparison tumor material of a new biopsy assessed locally has to be used, if possible. In cases of discordant *RAS* results between liquid and tumor biopsy, patients will not be randomized. Overall, in at least 80% of patients a biopsy should be taken to confirm *RAS* status in tissue of respective patients. However, if a patient refuses a new biopsy, he/she will still be randomized and can continue the study.

In addition, in the first 8 weeks after randomization, blood samples of the first 10 patients randomized into experimental arm A will be taken more frequently: at weeks 2, 4, 6 and 8 instead of just weeks 4 and 8. If ≥ 5 of 10 patients in the experimental arm A show *RAS* mutation within 4 weeks after randomization by liquid biopsy, the study may be terminated prematurely, because, in this case, the effect of *RAS* conversion does not seem to be lasting long enough.

Results of these analyses will be reviewed by a Data and Safety Monitoring Board (DSMB) and notified to the ethics committee together with recommendations of the DSMB regarding study conduct.

2. After 50 patients have been screened, the proportion of patients with conversion from *RAS* mutant to *RAS* wild-type will be analyzed and evaluated by the DSMB. If less than 50% of analyzed patients show conversion to *RAS* wild-type, the DSMB will make recommendations regarding the conduct of the study. These will be notified to the ethics committee.

3 Investigational Plan

3.1 Overall Study Design and Plan

This is an open-label, prospective, randomized, multicenter phase II trial to evaluate the efficacy and safety of intermittent addition of cetuximab to a FOLFIRI-based 1st-line therapy in patients with *RAS*-mutant mCRC at diagnosis who convert to *RAS* wild-type by monitoring the *RAS* mutation status by liquid biopsy.

Patients with left-sided *RAS*-mutated metastatic colorectal cancer (mCRC) eligible for study participation and receiving standard FOLFIRI as 1st line treatment will be screened for a maximum of 3 months (week 4 to 16) for conversion to *RAS* wild-type. As soon as *RAS* wild-type is detected, no further blood samples for screening will be taken. Conversion to *RAS* wild-type at week 4 or 8 and at week 12 or 16 will lead to randomization at weeks 8 or 16 (directly after follow-up CT scan), respectively. Patients will be randomized 1:1 into experimental Arm A (switch arm) or control Arm B.

For patients without conversion to *RAS* wild-type by week 16, the 'end of study' form must be completed.

Figure 1 gives an overview of study design.

[figure not shown]

Figure 1: Overview of study design

For the safety of the patients, 2 stopping rules are included:

[figure not shown]
1. After randomization of 20 patients, further enrollment into the study will be paused. For the first 20 patients with *RAS* wild-type result in liquid biopsy during screening this result should be confirmed by new tumor biopsy assessed locally, if feasible. If results between the methods are discordant, the patient cannot be randomized and the 'end of study' form must be filled in. Overall, in at least 80% of patients a biopsy should be taken to confirm *RAS* status in tissue of respective patients. However, if a patient refuses a new biopsy, he/she will be randomized and can continue the study. Also, analysis of blood samples from the first 20 screened patients will be analyzed in parallel by 2 laboratories. An overview of planned examinations for the first 20 patients is given in Figure 2 (before randomization) and Figure 3.

In addition, in the first 8 weeks after randomization, blood samples of the first 10 patients randomized into experimental arm A will be taken more frequently: at weeks 2, 4, 6 and 8 instead of just weeks 4 and 8. If ≥ 5 of 10 patients in the experimental arm A show *RAS* mutation within 4 weeks after randomization by liquid biopsy, the study may be terminated prematurely, because, in this case, the effect of *RAS* conversion does not seem to be lasting long enough.

Results of all analyses will be forwarded to the DSMB which will assess the data and will provide recommendations for study conduct. Results and recommendations of the DSMB will be notified to the ethics committee.

2. After 50 patients have been screened, proportion of patients with conversion from RAS mutant to RAS wild-type will be analyzed and evaluated by the DSMB. If less than 50% of analyzed patients show conversion to RAS wild-type, the DSMB will make recommendations regarding the conduct of the study. These will be notified to the ethics committee.

For the first screened 20 patients:

For the first 20 patients with conversion to RAS wild-type during screening:

[figure not shown]

Figure 2: Overview of RAS analysis for the first 20 screened patients and for the first 20 patients with conversion to RAS wild-type

3.1.1 Blood Sampling for RAS Analysis

All RAS analysis by liquid biopsy is performed at a central laboratory by ddPCR.

Blood samples for liquid biopsy will be collected at the time points indicated in Figure 3 and in the 'Schedule of visits and assessments'. At each time point, 20 ml blood will be taken into STRECK BCT tubes and sent for central analysis to:

Immunologisch-Molekularbiologisches Labor
 Medizinische Universitätsklinik, Ruhr-Universität Bochum
 Universitätsklinikum Knappschaftskrankenhaus Bochum GmbH
 [name]
 [name]
 Germany

The central laboratory will forward cfDNA from blood samples of the first 20 screened patients for additional analysis to the second laboratory (Institut für Klinische Chemie, [name], [name]). However, randomization will be based on results of central laboratory only.

[figure not shown]

Figure 3: Time points of blood sampling

* At first, blood sampling at week 2 and 6 will be performed for the first 10 patients in Arm A; However, it may be continued for further patients due to recommendations of the DSMB.

Participating centers will be provided with STRECK BCT tubes, labels and packaging material. Shipment is free of charge for the participating centers and will be carried out by express delivery "GO! Express & Logistics".

Shipment of blood samples is possible from Monday to Thursday to ensure RAS analysis in a timely manner.

Instructions for blood sampling, labelling and shipment will be given to the centers with the investigator site file.

The central laboratory will document the results of the *RAS* analysis in the eCRF within 3-4 days for blood samples from the pre-randomization phase and within 1 week for blood samples taken after randomization.

3.1.2 Randomization

All enrolled patients with conversion of mutant *RAS* as estimated centrally by liquid biopsy of cfDNA within the first 4 months (weeks 4 to 16) and without PD as determined by CT scan will be randomized at week 8, for patients converting at week 4 or 8, and at week 16 for patients converting at week 12 or 16 directly after the CT scan in a 1:1 ratio to either experimental Arm A (switch arm) or control Arm B. Patients with progressive disease before the randomization will not be considered for randomization.

The randomization lists will be kept in safe and confidential custody at Alcedis GmbH.

Stratification factors for randomization are:

- Conversion to *RAS*-wt: ≤ 8 weeks vs. > 8 weeks

Randomization of a patient during pre-randomization phase will be performed automatically, at weeks 8 or 16, if centrally assessed *RAS* wild-type in liquid biopsy is documented by the central analysis laboratory before 8 weeks or after 8 weeks, respectively, and there is no disease progression at that time. Randomization result is notified immediately by an automatically generated fax to the investigator.

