Procedures / Assessments										
Change in or new concomitant medication		X (before study treatment administration)	X			X				
New tumor therapy									X	X
Survival data									X	X

* Every 8 weeks during the first year, thereafter every 12 weeks up to end of study duration of 36 months

** 3-monthly follow-up visits until end of study duration of 36 months; phone calls will count as study visits.

*** The results of RAS status, assessed locally, in tumor biopsy must be available within 10 days after the results of liquid biopsy become known. No randomization in case of different results for RAS status in tumor and liquid biopsy. 'End of study' form must be filled in for this case. Overall, in at least 80% of patients a biopsy should be taken to confirm RAS status in tissue of respective patients.

1) Blood samples from pre-screening/baseline will be analyzed only in cases with RAS wild-type in liquid biopsy at week 4 after starting FOLFIRI/mFOLFIRI. In patients who receive 1 -2 cycles FOLFIRI/mFOLFIRI in the pre-screening phase, the blood sample should be taken before administration of these cycles.

2a) Before randomization: Blood samples for liquid biopsy until detection of RAS wild-type at week 4, 8, 12 and 16 after starting FOLFIRI/mFOLFIRI .

2b) After randomization into the experimental arm: For the first 10 randomized patients only, blood samples for liquid biopsy at week 2, 4, 6 and 8 after starting FOLFIRI/mFOLFIRI; for subsequent patients at weeks 4 and 8; thereafter, for all patients, every 8 weeks for the first year, and every 12 weeks for the remaining study period. If receiving FOLFIRI/mFOLFIRI + cetuximab and disease progression is detected on CT and prior ctDNA analysis was wild-type, a single ctDNA analysis should be performed at the time of disease progression.

3) Body temperature, heart rate, blood pressure, weight and height (only at baseline)

⁴⁾ Previous medication taken within the last 2 weeks before date of informed consent has to be recorded.

⁵⁾ If clinically indicated, more ECGs should be performed during study

⁶⁾ CT scan: abdomen, chest and pelvis. In cases of contraindicated CT scan (e.g. contrast medium allergy) the MRI should be performed. The same method should be used throughout the study.

⁷⁾ Every 8 weeks ± 3 days

⁸⁾ Hemoglobin, thrombocytes, leukocytes, neutrophils (within 2 days before administration of study treatment)

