- Hematological and biochemical laboratory assessment including hemoglobin, thrombocytes, neutrophils, Na^+ , K^+ , Mg^{2+} , Ca^{2+} , ASAT, ALAT, alkaline phosphatase, GGT, bilirubin, urea, creatinine, creatinine-clearance, C-reactive CRP, CEA, CA-19-9

Prior the first cycle (within 72 h before administration of study treatment):

- Females of childbearing potential: urine pregnancy test (β -hCG)

Prior to administration of study treatment:

- Assessment of ECOG performance
- Survey of concomitant medication
- Vital signs: body temperature, heart rate, blood pressure, and weight

Every 2 weeks:

- Administration of study treatment (FOLFIRI or mFOLFIRI)
Patients with partial DPD deficiency should receive the first cycle with a reduced 5-FU dose. Dose reduction and escalation are at the discretion of the investigator and must be determined in the best interest of the patient.

Every 4 weeks:

- Females of childbearing potential: urine pregnancy test (β -hCG)

After every cycle:

- Assessment of adverse events. Adverse events are recorded according to NCI-CTCAE v.5.0. Serious adverse events have to be reported within 24 h to Alcedis GmbH (section 9.6)

Every 8 weeks:

- Tumor assessment using CT-scan (in case of contraindications to CT scan, e.g. allergy to contrast medium, MRI should be performed) and classification of the response according to RECIST-Criteria V 1.1; the same method should be used throughout the study

At week 4, 8, 12 and 16 (until conversion to RAS wild-type):

- Blood sample (20 ml) for liquid biopsy

If clinically indicated: ECG

For patients without conversion to RAS wild-type by week 16, the 'end of study'-form must be completed.

Patients with conversion of RAS mutation to RAS wild-type, by ≤ 8 weeks or by > 8 weeks, will be randomized at week 8 or 16 respectively. Before randomization, the inclusion / exclusion criteria have to be checked.

For the first 20 patients with *RAS* wild-type in liquid biopsy: New tumor biopsy, if possible, with *RAS* analysis. Overall, in at least 80% of patients a biopsy should be taken to confirm *RAS* status in tissue of respective patients.

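### The automatic randomisation trigger in Protocol 3.1.2 runs on the laboratory's documentation date, so a nominal week-8 converter cannot be randomised at week 8 as the same section requires

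*Protocol*

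**What the plan says.** Protocol 3.1.2 contains two rules.

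- **Visit rule.** A converter "will be randomized at week 8, for patients converting at week 4 or 8", and at week 16 for conversion at week 12 or 16, immediately after that visit's CT. Section 3.1 says the same ("wild-type at week 4 or 8 and at week 12 or 16 will lead to randomization at weeks 8 or 16"), as do the synopsis, Protocol 7.2 ("by ≤ 8 weeks or by > 8 weeks, will be randomized at week 8 or 16 respectively") and SAP 4.3.2.
- **Automatic trigger.** Randomisation "will be performed automatically, at weeks 8 or 16" if there is no progression and wild-type is "documented by the central analysis laboratory before 8 weeks or after 8 weeks, respectively".

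The only stratification factor is time of conversion, "≤ 8 weeks vs. > 8 weeks". Section 10.3 describes it in the same terms for the Cox model.

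On timing, section 3.1.1 has the central laboratory enter results "within 3-4 days for blood samples from the pre-randomization phase", with shipment on Monday to Thursday only. For the first 20 converters, tissue RAS status "must be available within 10 days after the results of liquid biopsy become known" (Schedule of visits, footnote ***). A discordant tissue result bars randomisation (same footnote; sections 2.7 and 3.1). A patient who refuses the new biopsy is still randomised.

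**The concern.** The visit rule goes by when the patient converts. The trigger goes by when the laboratory records the conversion. For samples at weeks 4 and 12 the two give the same answer. For a sample at week 8 they do not, and the trigger is the rule that the randomisation system would execute.

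Three things are at stake:

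- A week-8 converter may be held for 8 weeks and lost if the disease progresses.
- Section 3.1 stops screening samples once wild-type is found, so the deferred patient is randomised on an 8-week-old result. Under the visit rule the result is at most 4 weeks old. Result age matters in this trial: section 3.1 treats return of the mutation within 4 weeks of randomisation in at least 5 of 10 Arm A patients as possible grounds for stopping.
- The trigger omits the tissue condition that other sections impose on the first 20 converters.

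**Working it through.** **The plan's own figure.** ln(0.5)/ln(0.3) = 0.5757, as stated. For two-sided 5% and 80% power, Freedman's formula gives 109 events (power at 107 events 79.5%) and Schoenfeld's gives 103 (81.5%). With 58 per arm, exponential PFS, uniform 18-month accrual and 0.25% monthly drop-out, expected events at 52 months are 107.03. The stated 107 is reproduced, and none of its inputs involves the trigger.

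**Day arithmetic.** Inputs are samples at weeks 4, 8, 12 and 16 (Schedule footnote 2a), 3-4 days for the laboratory (3.1.1), and at most 10 further days for tissue (footnote ***). Randomisation is on day 56 or 112 (3.1.2). The start of the laboratory clock is not stated; I count from sampling.

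| Sample | Laboratory result (+3 to 4) | Tissue, latest (+10) | Day under visit rule | Laboratory margin | Tissue margin | Literal trigger |
|---|---|---|---|---|---|---|
| Week 4, day 28 | 31-32 | 41-42 | 56 | 24-25 days early | 14-15 days early | week 8 |
| Week 8, day 56 | 59-60 | 69-70 | 56 | 3-4 days late | 13-14 days late | week 16 |
| Week 12, day 84 | 87-88 | 97-98 | 112 | 24-25 days early | 14-15 days early | week 16 |
| Week 16, day 112 | 115-116 | 125-126 | 112 | 3-4 days late | 13-14 days late | week 16, already past |

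**Sensitivity to windows.** The CT has a ±3 day window. With the CT on day 59, a 3-day result just arrives and a 4-day result does not. If blood could also be drawn 3 days early (an assumption, since no sampling window is stated), the result comes on day 53 + 3 or 4 = 56-57. That is in time for a day-59 CT but still not before week 8, and tissue could take until day 67. Even same-day documentation of a day-56 sample is at week 8, which the trigger puts in neither category.

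**Cost of an 8-week deferral.** With λ = −ln(S12)/12 per month and t = 56/(365/12) = 1.841 months, the probability of progression or death is 1 − exp(−λt).

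- S12 = 30% (planning control rate): λ = 0.1003; 1 − exp(−0.1847) = 16.9%.
- S12 = 50%: λ = 0.0578; 10.1%.
- S12 = 25%: λ = 0.1155; 19.2%.

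These carry a post-randomisation planning hazard back into the screening period, so they are illustrations.

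**The case against.** The best defence is that the trigger sentence is loose shorthand for the visit rule. The synopsis, sections 3.1 and 7.2, the opening of 3.1.2 and SAP 4.3.2 all send week-8 converters to week 8, and one sentence should not override them. The laboratory time is also an upper limit, not a minimum. Both points are fair. But the shorthand reading does not close the gap: if the full turnaround is used, the week-8 or week-16 result does not exist when the patient is to be randomised right after the CT. No section says what happens then.

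On tissue, the condition is stated in several places, and section 7.2 requires the eligibility criteria to be checked before randomisation. Randomising a discordant patient would therefore breach the protocol. That stands. The remaining fault is that the automatic trigger does not carry the condition. Nor is the check late in general: week-4 and week-12 converters have two weeks in hand, ten days is a maximum, and patients without a new biopsy are unaffected.

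The delay and the late tissue result cannot both hit the same week-8 patient. Deferral to day 112 leaves ample time for tissue due by about day 70; randomisation at week 8 removes the deferral.

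A reader might infer that week-8 converters are placed in the wrong stratum. The documents do not support this. Sections 3.1.2, 7.2 and 10.3 define the stratum by conversion, and nothing says that the system derives it from the trigger. A count of affected patients cannot be given either. The documents do not state how conversions spread over the four tests, and section 2.4 reports conversion after a single cycle, which argues against an even spread.

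**Conclusion.** The point holds as an internal contradiction in 3.1.2. For a sample drawn at nominal week 8, the trigger as written cannot produce the week-8 randomisation that the same section requires. Taken literally it defers the patient by 8 weeks, with about a 17% chance of becoming ineligible meanwhile (10-19% over the range shown, if the planning hazard applies before randomisation). At week 16 trigger and stratum agree, but the result may come 3-4 days after the last randomisation point. For re-biopsied week-8 or week-16 converters among the first 20, the tissue result may come about 14 days after the randomisation visit.

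A reader might also infer a biased treatment comparison or a shortfall in power. Neither follows. Everything here happens before allocation, screening continues until 116 patients are randomised, and the 107 events are unchanged. SAP 4.2 reports enrolment closed at seven patients, and SAP 4.14 and 4.19 provide for no covariates and no significance level, so the final report's analysis is not affected.

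**What to change.** Reword the trigger in 3.1.2 in three parts:

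1. Randomisation visit and stratum both follow the collection date of the first wild-type sample: week 4 or 8 is ≤ 8 weeks, week 12 or 16 is > 8 weeks.
2. Randomisation opens once that visit's CT and the laboratory result are both recorded.
3. For the first 20 converters, automatic randomisation is held until the tissue result, or refusal or infeasibility of the biopsy, is recorded.

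The cost is a text change and a change to the system trigger. Randomisation would fall a few days after the CT for week-8 and week-16 converters, and up to about two weeks after it for the affected first-20 patients. Sample size and event target stay as they are.

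With enrolment closed, the practical step is for the final report to state which rule the system applied. Sampling, analysis and randomisation dates are already planned in SAP Listings 3, 20.1 and 20.3. Any reuse of the design should carry the reworded trigger.

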3.1.3 Blinding

Not applicable.

3.1.4 Number of Patients

Estimated number of patients enrolled into pre-randomization phase (conversion rate of 80%): 144

Number of randomized patients: 116 (58 patients in each arm) with 107 required events.

The screening will be continued until randomization of 116 patients.

3.1.5 Planned Study Timelines

Duration of recruitment: 18 months at a rate of 8 patients/month (counted from first patient in (FPI)).

Follow-up from last patient in (LPI) to end of safety follow up: 1 month after last administration of up to 36 months of study treatment.

Further follow-up for survival until trial termination: 4.5 years after FPI.

Expected total trial duration: 4.5 years

3.2 Study Objectives

The aim of this randomized study is to evaluate whether patients with left sided *RAS*-mutant mCRC at diagnosis will derive a benefit from the adaptation of adding cetuximab to 1st line therapy (FOLFIRI) after *RAS*-mutation status has changed to wild-type and changing back to

FOLFIRI, as required if RAS-mutation status has changed to mutant, depending upon, and monitored by, longitudinal ctDNA liquid biopsies.

3.2.1 Primary Objective

The primary objective is to evaluate efficacy in terms of progression free survival (PFS) from the date of randomization in the study according to Response Evaluation Criteria in Solid Tumors (RECIST) version 1.1 criteria in experimental and control arms

